Study aims and primary and secondary outcomes

The study has three aims.

1. Among 450 (18-24 y.o) JIY in BJI randomized to either Link2CARE or standard of care (SOC), to determine **the efficacy of Link2CARE** delivered by STAY staff embedded within BJI on (a) HIV outcomes: HIV testing/repeat testing; HIV risk behaviors; (b) STI outcomes: STI testing/repeat testing; linkage to care of JIY with STIs; (c) SU outcomes: SU screening; SU; linkage to care of JIY with SU/D; and (d) (exploratory) linkage to care of HIV+ youth and linkage to PrEP for (behaviorally) eligible HIV- youth.
2. To determine **the influence of theoretically-based mechanisms of change of Link2CARE** (e.g., predisposing characteristics, enabling resources, perceived need, organizational climate; staff attitudes) on the proposed HIV, STI and SU outcomes.
3. To describe Link2CARE implementation and elucidate the **system/organizational-, staff-, and youth-level factors that influence implementation (i.e. acceptability, sustainability, feasibility) of Link2CARE in an ASP** to develop a plan for dissemination and scale-up of Link2CARE in New York City

The study has the following primary, secondary, and exploratory outcomes (related to aim 1)

Domain 1 (primary outcomes: HIV outcomes): (a) total number of unprotected anal and vaginal sex occasions in past three months at 12 month FU; (b) acceptance of HIV testing at initial offering (y/n), (c) any HIV

testing between 6-month and 12-month FU (y/n).

Domain 2 (secondary outcomes: SU outcomes): (a) frequency of youth substance use in past 30 days at 3-, 6- and 12-month FUs; (b) number of youth referred to SU treatment at 3-, 6- and 12-month FUs; at (c) number of youth attending intake plus one treatment session at 3-, 6- and 12-month FUs.

Domain 3 (secondary outcomes: STI testing outcomes): (a) acceptance of STI testing at initial offering (y/n), (b) any STI testing between 6-month and 12-month follow up; (c) number of STI+ youth referred to STI treatment at 3, 6, and 12 months FUs; (d) number of STI+ youth attending ≥ 1 treatment appointment at 3, 6, 12 months FUs.

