Based on our previous work, the retention rate for studies of JYI was about 75% to 80%. Even though we anticipate being able to maintain 20% attrition, we conservatively use 25% attrition at 12-month FU in this power calculation. Under such assumptions and with a baseline sample of 450 participants, we estimate a final sample of at least n=338 with complete data for the primary analysis at 12-month FU. With 169 participants per group and the use of Bonferroni correction, we will be able to provide 80% power to detect a standardized effect size of .35 or more on any of the three primary outcomes (i.e., total number of unprotected anal and vaginal sex occasions in past three months, acceptance of HIV testing at initial offering; and frequency of substance use in past 30 days). The standardized effect size of .35 is considered as a relatively small to moderate effect size according to Cohen⁴ and our previous study suggests that it is an achievable effect. A substantial increase in sample size will not strongly impact effect size – e.g. to reduce the standardized effect size from .35 to .32, 100 more participants (22% increase in current sample size) would be required. Even if actual attrition is greater than expected e.g. say 30%, the detectable standardized effect size will only increase slightly to .36. Furthermore, as we will impute missing data using informative covariates for the primary analyses and using a less conservative Holm procedure for multiple comparison adjustment, power to detect such effects will actually be greater than 80%.

Table 1. Inclusion/exclusion criteria

Study Phase	Study Sample	Inclusion Criteria	Exclusion Criteria
Phase 1: Adaptation for Link2CARE	Peer advisory panel n=14	1) Between 18-24 years of age 2) Currently enrolled in BJI 3) Conversant in English (in the past two years, only two JIY at BJI have required language assistance).	1) Medical or psychiatric illness requiring hospitalization 2) Serious suicidal or homicidal ideation
	BJI staff n=6	1) Currently employed at BJI	None
Phase 2: Link2CARE Efficacy Trial and Implementation Evaluation	Pilot Youth n=8	1) Between 18-24 years of age 2) Currently enrolled in BJI 3) Conversant in English (in the past two years, only two JIY at BJI have required language assistance).	1) Medical or psychiatric illness requiring hospitalization 2) Serious suicidal or homicidal ideation

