Intent-to-treat principles will be invoked in the primary analysis. The primary aim is to determine whether participants randomized to Link2CARE show greater improvement in HIV outcomes from baseline to 12-month follow up than participants in SOC. Measurement of primary HIV outcomes includes three variables: number of unprotected sex occasions, whether participants accept HIV testing at initial offering (y/n), and any (repeat) HIV testing between 6-month and 12-month follow up (y/n). Other behavioral and linkage variables to be examined as secondary and exploratory outcomes are described in Section 3.3.9.3. Implementation outcomes to be examined include feasibility, acceptability, and sustainability. In addition, we will examine potential CFIR correlates of implementation, such as organization culture and climate and staff attitudes. Finally, mediators associated with service use as specified by the Andersen model will be examined, including motivation for treatment, perceived barriers to treatment, prior service utilization.

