Analysis plan for Specific Aim 1. Prior to conducting our multivariable analyses, we will examine study variables using descriptive statistics, testing for differences across demographic characteristics (e.g., race/ethnicity, age) using t-tests, ANOVAs, and Chi-squares, as appropriate. Systematic baseline differences are not expected; however, any parameters that differ across conditions at baseline will be included as covariates in subsequent models. We will calculate descriptive summary statistics corresponding to study variables at each follow-up (FU) to understand any temporal patterns, as well as compare the two groups in terms of average change from baseline to 12-months post-baseline. We will use the general framework of generalized linear models (GLM) to model the longitudinal outcome trajectories and GEE method to account for within-subject correlation across the four time points (baseline, 3-, 6-, and 12-months). Stratified randomization of participants to the groups based on their gender requires that the analysis also include gender as covariate. The general form of the analysis model will be $g(\mu) = \alpha_0 + \alpha_1 X + \beta I + \sum \gamma_i T_i + \sum \delta_i T_i I$, where g denotes the link function (identity for continuous outcome, logit for binary outcome and natural log for count outcomes) X represents the indicator of female (vs. male), I is the group indicator for Link2CARE (vs. SOC), and T_i is the indicator for time at 3-month, 6-month, and 12-month evaluation (vs. baseline) for $i=1, 2, \text{ and } 3$. The interaction coefficients δ_i are of interest, measuring the difference in the rate of change in outcome across the two treatment groups at each follow-up assessment. We will employ the above analytic approach to examine differences between youth in Link2CARE and in the SOC condition with respect to key study parameters within these four domains detailed below. Proposed hypotheses are that the experimental arm (Link2CARE) would have better outcomes (e.g. greater reduction on total number of unprotected anal and vaginal sex occasions in past three months from baseline to 12 month FU; greater increase in proportion of acceptance of HIV testing at initial offering; greater reduction on frequency of substance use in past 30 days at 3-, 6- and 12-month FUs; and of those referred to SU treatment, a greater number of youth attending intake plus one treatment session at 3-, 6- and 12-month FUs)

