compared to the standard of care; all hypothesis tests will be conducted under the control of familywise error rate no greater than 0.05 level. The Holm step down procedure will be employed to adjust for multiple comparisons.

1. **Domain 1 (primary outcomes: HIV outcomes):** (a) total number of unprotected anal and vaginal sex occasions in past three months at 12 month FU; (b) acceptance of HIV testing at initial offering (y/n), (c) any HIV testing between 6-month and 12-month FU (y/n).
2. **Domain 2 (SU outcomes):** (a) frequency of youth substance use in past 30 days at 3-, 6- and 12-month FUs; (b) number of youth referred to SU treatment at 3-, 6- and 12-month FUs; at (c) number of youth attending intake plus one treatment session at 3-, 6- and 12-month FUs.
3. **Domain 3 (exploratory outcomes: HIV/PrEP linkage outcomes):** (a) number of HIV+ youth referred to HIV treatment at 3, 6, and 12 months FUs, (b) number of HIV+ youth attending at least one treatment appointment at 3, 6, and 12 months FUs; (c) number of youth behaviorally PrEP eligible referred to PrEP/medical care at 3, 6, and 12 months FUs, (b) number of youth behaviorally PrEP eligible attending at least one HIV care appointment care at 3, 6, and 12 months FUs.
4. **Domain 4 (STI testing outcomes):** a) acceptance of STI testing at initial offering (y/n), (b) any STI testing between 6-month and 12-month follow up; (c) number of STI+ youth referred to STI treatment at 3, 6, and 12 months FUs; (d) number of STI+ youth attending ≥ 1 treatment appointment at 3, 6, 12 months FUs.

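### The unprotected-sex count is tested as a difference in change from baseline; adjusting for the baseline count would test the same 12-month effect with more power at no extra data cost

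*Combined protocol and SAP*

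**What the plan says.** The section on study aims and outcomes defines the first primary endpoint as the "total number of unprotected anal and vaginal sex occasions in past three months at 12 month FU". The opening of the Data analysis plan states the aim as change: whether Link2CARE participants "show greater improvement in HIV outcomes from baseline to 12-month follow up than participants in SOC". The Specific Aim 1 hypothesis matches that aim: "greater reduction on total number of unprotected anal and vaginal sex occasions in past three months from baseline to 12 month FU".

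The Aim 1 model uses the "GEE method to account for within-subject correlation across the four time points (baseline, 3-, 6-, and 12-months"), so baseline is one of the response times. It has a gender term, a free arm term, time indicators and arm-by-time interactions, with a log link for counts. The interactions are the parameters of interest, "measuring the difference in the rate of change in outcome across the two treatment groups at each follow-up assessment".

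Gender is the only covariate fixed in advance. Beyond that, "any parameters that differ across conditions at baseline will be included as covariates in subsequent models". The baseline count is not named. The baseline interview is planned in all 450 youth (Data acquisition, entry and transmission).

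The Sample size and power section claims "80% power to detect a standardized effect size of .35 or more on any of the three primary outcomes", with 169 per group and a Bonferroni correction. It does not say which SD standardizes .35 and gives no baseline-to-12-month correlation.

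**The concern.** With a free arm term at baseline, the 12-month interaction is the arm difference at 12 months minus the arm difference at baseline. Randomization makes the expected baseline difference zero, so subtracting it leaves the target unchanged and adds the sampling error of the baseline means. If baseline and 12-month counts are only moderately correlated, the added error outweighs the benefit, and the test can be weaker than one that ignores baseline. Adjusting for the baseline count uses the same data and subtracts only the part of the baseline difference that predicts the 12-month outcome.

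At stake is power on one of three co-primary outcomes, in a trial whose sample size gives about 80% before any such loss.

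**Working it through.** **Inputs from the documents.** 169 completers per arm, 225 randomized per arm (450, 1:1), effect .35, 25% attrition (Sample size and power); two-sided alpha 0.05/3, critical value 2.394 (Trial Stopping Rules).

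**Inputs assumed.** The correlation rho, the ratio k of baseline SD to 12-month SD (1 unless stated) and, for the simulations, mean count, spread and rate ratio. The documents give none of these.

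**1. The plan's own figure.** As a plain two-group comparison, power = Φ(0.35/√(2/169) − 2.394) = Φ(3.217 − 2.394) = 79.5%. The same formula gives a detectable effect of 0.365 at 30% attrition and 0.319 with 100 more participants, in line with the plan's .36 and .32. No correlation enters any of these figures.

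**2. Variance on a linear scale.** In 12-month SD units, per participant:
- change from baseline: 1 + k² − 2k·rho
- baseline-adjusted: 1 − rho²
- gap: (k − rho)², never negative

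With k = 1 the relative efficiency of change is (1 − rho²)/[2(1 − rho)] = (1 + rho)/2.

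**3. Power.** Power = Φ(d/√(2v) − 2.394), with v the per-arm variance:
- change, complete pairs: 2(1 − rho)/169
- change, all 225 baselines used, endpoints missing at random: (1 − rho²)/169 + (1 − rho)²/225
- baseline-adjusted: (1 − rho²)/169

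Worked example, rho = 0.3: complete-pairs change has v = 0.00828, so Φ(2.719 − 2.394) = 62.7%; adjusted has v = 0.00538, so Φ(3.373 − 2.394) = 83.6%.

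With .35 in 12-month SD units (d = 0.35):

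| rho | Change, complete pairs | Change, all baselines | Adjusted | Efficiency (pairs / all baselines) |
|---|---|---|---|---|
| 0.2 | 56% | 61% | 81% | 60% / 67% |
| 0.3 | 63% | 67% | 84% | 65% / 71% |
| 0.4 | 71% | 75% | 87% | 70% / 76% |
| 0.5 | 79.5% | 82% | 91% | 75% / 80% |
| 0.6 | 89% | 90% | 95% | 80% / 84% |
| 0.7 | 96% | 97% | 98% | 85% / 88% |

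The change contrast equals a 12-month-only comparison at rho = k/2 in complete pairs (0.50 for equal SDs; 0.40 to 0.625 for k from 0.8 to 1.25), and at 0.46 with all baselines and equal SDs.

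With .35 in SD-of-change units (d = 0.35·√(2(1 − rho))), change has 79.5% power at any rho in complete pairs and 82-84% with all baselines for rho 0.2 to 0.5. Adjusted power is 96%, 94%, 93% and 91% at rho 0.2, 0.3, 0.4 and 0.5, and 86% at 0.7.

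**4. Check on the log link.** Lognormal-Poisson counts were simulated with 225 per arm, 25% missing at random, mean 8, log-scale SD 1, rate ratio 0.62, robust SEs and 3,000 trials per setting. The planned model was an exchangeable GEE using all baselines, with baseline and 12 months only and gender omitted.

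| Count correlation | Planned | Adjusted | Baseline difference constrained to zero |
|---|---|---|---|
| 0.22 | 65% | 82% | 82% |
| 0.39 | 75% | 87% | 87% |
| 0.58 | 91% | 96% | 95% |

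Null rejection (nominal 1.67%) was 1.6-2.2% planned, 2.1-2.3% adjusted and 2.1-2.2% constrained. A separate simulation (169 complete pairs per arm, rate ratio 0.6, 600 runs) gave 60% against 82%, 70% against 86% and 90% against 94% at count correlations 0.27, 0.45 and 0.67. Both analyses estimated practically the same log rate ratio (about −0.51 to −0.52).

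**The case against.** The strongest reply is that nothing here is an error. The aim and hypothesis are worded as change from baseline, the interaction tests exactly that, and the test is unbiased. Nor is a power shortfall proved: if .35 is in SD-of-change units, a natural reading for a plan that tests change, the stated 80% holds. The low figures need 12-month SD units and rho below about 0.5 together. At rho 0.7 the gain on that basis is only about 2 points. All of this stands, and it makes the point one of efficiency and reporting. But adjustment gains power on either SD basis.

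Other objections carry less weight:
- **Imputation and Holm.** The plan expects both to raise power. Imputing missing endpoints does not remove the free baseline arm term, and Holm applies to either analysis. The simulations did not impute, used two time points and omitted gender, so their percentages illustrate the comparison and are not the power of the exact planned analysis.
- **Log link.** The never-worse result is derived on a linear scale; for counts the support is simulation. Slightly liberal standard errors may explain a little of the simulated gain, but not gaps of 5 to 17 points.
- **Order of procedures.** The data acquisition section mentions randomization before baseline assessment. This does not show that allocation influenced baseline answers, but the order should be confirmed, especially before constraining the baseline arm difference to zero.

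**Conclusion.** The concern holds. The planned test of the count is valid but gives up precision that the baseline data could recover. With equal SDs and complete pairs, its efficiency relative to baseline adjustment is 60-75% for rho 0.2 to 0.5 (67-80% if all baselines are used), rising to 85% at 0.7 in complete pairs. In power, the gain at rho 0.2 to 0.5 is about 8 to 25 points if .35 is in 12-month SD units, and about 8 to 17 points if it is in SD-of-change units, across the complete-pairs and all-baselines cases. It shrinks as rho rises.

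Whether the planned test reaches the stated 80% cannot be decided from the documents, because it turns on an unstated SD basis and correlation. The sizes rest on assumed rho, SD ratio, mean count and rate ratio; the direction on the linear scale does not. The point concerns the count only: acceptance of testing at first offer has no baseline value. The change should be made, but it is not a flaw that invalidates the trial.

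**What to change.** For the count, take either route:
- Model the 3-, 6- and 12-month counts with arm, time, arm-by-time, gender and the baseline count, for example log(count + 1), as pre-specified covariates, and test the arm effect at 12 months.
- Keep baseline as a response, constrain the baseline arm difference to zero and use an unstructured working correlation. This keeps the change-from-baseline framing. Confirm first that baseline answers are collected before allocation or cannot be affected by it.

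In the power section, state which SD standardizes .35 and the rho assumed.

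A separate, minor point that does not cause the power loss: the rule that adds covariates found to differ at baseline leaves the model unknown until data are seen. Replace it with a fixed list and show baseline tables descriptively.

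The cost is SAP wording and one sentence on power; no new data are needed. For scale, the plan says that moving the detectable effect from .35 to .32 would take 100 more participants. At rho 0.4, on the 12-month SD basis, adjustment moves it from 0.37-0.39 to 0.32 with none.

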**Health and Justice: A Continuum of Care for HIV and SU for
Justice-Involved Young Adults (PHASE 2)**

NCT03369249

Study Protocol and Statistical Analysis Plan

(10/20/17)

**Health and Justice: A Continuum of Care for HIV and SU for Justice-involved Youth
(R01 DA 043122)**

**Principal Investigator:
[name]., Columbia University and New York State Psychiatric Institute**

Project Overview

Statement of Responsibility for developing and executing DSMP

The Principal Investigator accepts full responsibility for the development and execution of this Data and Safety Monitoring Plan.

Brief protocol description and study design

This protocol concerns the adaptation, efficacy-testing and implementation evaluation of a multi-component service delivery model (Link2CARE) that aims to increase HIV/STI testing and substance use (SU) screening; reduce HIV and SU risk; and increase linkage to HIV, STI and SU services in justice involved youth (JIY) who are enrolled in an alternative sentencing program (Brooklyn Justice Initiatives; BJI). We propose to adapt and integrate the following evidence-based strategies to create Link2CARE: (i) **Screening**: Offer an onsite rapid oral HIV test and STI urine test at intake into BJI and screen HIV risk behavior and SU; (ii) **Brief intervention**: use brief interventions (1-2 sessions) to reduce HIV risk and SU behavior and promote treatment/service readiness (*MOVE*¹ and *NYSBIRT*^{2,3}); (iii) **Linkage to HIV and SU care**: use a strengths-based patient navigator approach to mobilize JIY strengths and reduce barriers to treatment, while establishing formal relationships and referral protocols with service providers. We have initiated a partnership with BJI, which serves 9000 JIY annually, and Project STAY, a youth-focused, hospital- and community-based, health and HIV treatment program; Project STAY HIV testing outreach workers will be embedded into BJI to deliver Link2CARE. We will test the efficacy of Link2CARE in a randomized controlled trial among N=450 BJI-enrolled JIY (18-24 y.o.), randomized to either Link2CARE or standard of care (SOC) and conduct implementation evaluation to explore individual-, staff, and system-level influences on implementation of this new model to inform scale-up and dissemination. Youth will be assessed at baseline and 3-, 6-, and 12-months post-intervention. BJI and Project STAY staff will be assessed before launch of Link2CARE and 12 and 24 months later.

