DATA MANAGEMENT AND ANALYSIS

Data acquisition, entry and transmission

Study data will be collected in Phases 1 and 2. All Phase 1 and all baseline assessments (Phase 2) will be collected at BJI. Subsequent Phase 2 assessments will occur at BJI, in the participant’s home or at another agreed upon location. Note: BJI is not involved in survey administration, data entry and management, or data storage.

Phase 1: Advisory Panel data: Peer (n=14) and Staff (n=6) Advisory Panels will meet in a series of Panel workgroups during Phase 1 to provide feedback on the adaption of the SU and HIV interventions. Data from these Panel workgroups will be gathered in note form by work group facilitators and will not contain any participant identifying information. These data will be transcribed by research assistants and will be used between workgroups to inform adaptation of interventions.

Pilot data: n=8 youth who participate in a pilot of the SU and HIV protocols will complete paper-and-pencil process measures following the completion of the pilot which will be administered by human subject-trained research assistants (RAs). These research assistants will bring completed questionnaires to the research offices at NYSPI on the day of data collection. These data will be entered in an electronic database by human subject-trained research assistants. This database will be stored on password-protected computers in encrypted files. Researchers will retain the pilot process assessments until the completion of all project activities in Year Five when they will be destroyed following HIPAA standard document destruction services.

Phase 2: Substance use and HIV behavioral risk screen. Following randomization and baseline assessments, n=225 JIY randomized to Link2CARE will complete substance use and HIV behavioral risk screeners. Screening will take place at BJI in private rooms or other agreed upon location (for follow-up survey assessments). Data will be captured on encrypted, password protected computers, entered directly by human subjects-trained RA's into CiW using Sawtooth Software. Sawtooth Software allows for all standard question types, skip patterns, and data piping. Web-based data collection will **not** be used. Following interview completion, RAs will then transport interview data to NYSPI in the encrypted password protected computer, and immediately upload it upon return into the master database at NYSPI held on a secure server.

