Analysis plan for Specific Aims 2 and 3. Descriptive statistics will be computed to quantify implementation at every step, by participant and by provider. Thus, we will be able to compute uptake of LINK2CARE, dose/intensity of intervention received, number of providers delivering each intervention, and other implementation parameters. Of note for Aim 2, which seeks to examine the proposed mechanisms of change of the intervention on HIV, STI and substance use outcomes, a given outcome (e.g. HIV/STI testing uptake, or PrEP uptake or reduced substance use) of this analysis will only be examined among those for whom it is relevant. For example, if a youth does not meet criteria for PrEP and as such is not offered PrEP, we would not include this youth in analyses of mechanisms of change of Link2CARE as they influence substance use or PrEP uptake as an outcome. We will examine the changes in specific outcomes (e.g. sexual behavior post-intervention) as a function of proposed theory-based intervention mediators (e.g. predisposing characteristics, enabling resources, perceived need for treatment/services). We will use structural equation models for these analyses. Structural equation modeling is preferred to multiple regression techniques because of the potential measurement error in our mediating variables and because of the possible feedback between dependent and mediating variables. We will test the model described in Figure 1 in the application, entering intervention condition as exogenous variables and the mediating factors included in Figure 1 as endogenous variables. Prior to conducting the structural analyses, however, we will examine the effects of the intervention on the putative mediating variables; a condition for inclusion in the equation will be a significant intervention effect on the potential mediators. Using standardized path coefficients, we will examine the relative associations of mediators to behavior change. We will also examine the path coefficient for the direct effect of the intervention after removing the effects of mediating constructs. For example, Link2CARE may have a more positive effect on acceptance of HIV (and STI) testing among JIY with greater perceived HIV risk, greater motivation to receive services, or positive HIV-testing history. Similarly, Link2CARE may have more positive effect on linkage outcomes when operating in an ASP that is more supportive of concepts perceived as innovative by both BIJ and STAY staff. Here, organizational culture would appear to modify Link2CARE's impact on youth service referral and engagement outcomes. We will examine the Lagrange Multiplier and Wald Tests to consider the deletion or inclusion of paths⁵; ultimately, however, deletion or inclusion of paths will be informed by theoretical underpinnings. Once the model is identified, we will test for group differences between intervention conditions in latent constructs and in the proposed paths between these constructs. This method will allow us to estimate the intervention effects on the constructs directly as well as their relationships to one another.⁶ We will use three goodness-of-fit indices: Bentler-Bonnet's Normed Fit Index, Bentler-Bonnet's Non-Normed Fit Index, and the Comparative Fit Index. We will also verify the root mean-square error of approximation (RMSEA) as an index of misfit. Well-fitting models will have fit indices of .90 or higher and $< .06$ for RMSEA.

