
Analysis of participant attrition and missing data. We will make every effort to retain participants in the study to avoid bias due to attrition. For those individuals who refuse continued participation, we will document reasons for study discontinuation and Rubin's multiple imputation method with 11 repeated imputations will be

employed to impute the missing endpoint for conducting the intent-to-treat analysis.

QUALITY ASSURANCE

Procedures in place to ensure the validity and integrity of the data

All data collection protocols include a form on which research staff members record any problems with the data collection or unusual occurrences during the collection. They also are encouraged to bring problems to the attention of the Project Director, or PI. These members of the research staff also meet on a regular basis to identify and address any issues that arise. These procedures allow our research staff an opportunity to quickly review and respond to any possible concerns. We expect missing data to be minimal, nevertheless regular (quarterly) quality assurance checks will be made by the Project Director to identify any systematic missing information and remedies will be enacted.

Procedures to guarantee the accuracy and completeness of the data, during data collection, entry, transmission, and analysis.

To check for errors in data entry, we will adhere to the following protocol. All face-to-face surveys will be recorded. One out of every seven recordings for each interviewer will be compared to the entered interview. If we identify a proportion of errors that is more than 1% error, we will temporarily suspend the interviewer from active interviewing. We will listen to all interviews for comparison purposes, identifying any errors and will re-train the interviewer to ensure accuracy and completeness of all face-to-face survey interviews. A subset (10%) of all data from hard-copy/paper-pencil instruments that is entered into the project database will be similarly checked. If we identify a proportion of errors that is more than 1% error, we will reenter all questionnaires and subsequently compare both data sets. We will go back to the original surveys to resolve all inconsistencies. To prevent data entry problems we will prepare a data entry system that will alert us when data are entered that are out of range.

Procedures for preventing and addressing breaches of confidentiality

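### The substance use attendance hypothesis is worded among referred youth, a group formed after randomization, while the outcome itself has no such restriction; the Aim 1 comparison should be fixed on all randomized youth

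*Combined protocol and SAP*

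**What the plan says.** Three places describe the SU attendance outcome, and they differ on who is counted.

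- **Analysis plan for Specific Aim 1**, in its examples of hypotheses: "of those referred to SU treatment, a greater number of youth attending intake plus one treatment session at 3-, 6- and 12-month FUs".
- **Domain 2(c)**, worded identically in the Aim 1 domain list and under *Study aims and primary and secondary outcomes*: "number of youth attending intake plus one treatment session at 3-, 6- and 12-month FUs". There is no restriction to referred youth. The study aims section labels Domain 2 secondary.
- **Aim 1(c)**, under *Study aims*, speaks of linkage to care for youth with SU or disorder.

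Other statements bear on the choice without settling it:

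- *Data analysis plan*: "Intent-to-treat principles will be invoked in the primary analysis"; the variables then listed are the HIV outcomes. The same paragraph adds: "Other behavioral and linkage variables to be examined as secondary and exploratory outcomes are described in Section 3.3.9.3". No section with that number is in the document.
- *Analysis plan for Specific Aims 2 and 3*: a given outcome "of this analysis will only be examined among those for whom it is relevant". This is written for Aim 2.
- *Brief protocol description*: Link2CARE includes "establishing formal relationships and referral protocols with service providers".
- *Data acquisition, entry and transmission*: after randomization and baseline, "n=225 JIY randomized to Link2CARE will complete substance use and HIV behavioral risk screeners". The passage describes this screener for that arm only.

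**The concern.** Randomization protects a comparison of everyone assigned to each arm. It does not protect a comparison of youth who were later referred, because the arms may refer different numbers and kinds of youth. Referral is a result of assignment here: it is outcome Domain 2(b), Link2CARE is built to increase linkage, and its screener is described only for Link2CARE youth.

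The Aim 1 model is a generalized linear model with GEE, fitted to individual youth over time. Someone must decide which youth enter it for Domain 2(c). Taken literally, the hypothesis admits only referred youth. Any gain from referring more youth then drops out of the comparison. If the additional referrals are less motivated on average, Link2CARE can look no better, or worse, while more of its randomized youth reach treatment.

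**Working it through.** **1. The plan's own figure.** No power is stated for Domain 2(c). The stated 80% for the primary outcomes (169 per group, standardized effect 0.35, alpha 0.05/3 two-sided) does reproduce: the normal approximation gives 79.5%, and the detectable effect is (2.394 + 0.842) × √(2/169) = 0.352. Nothing in it depends on the disputed wording.

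**2. A hand check (assumed rates).** Suppose 20% of youth are referred in either arm and half of them attend. Link2CARE refers a further 20%, of whom a quarter attend. It has no effect on attendance once a youth is referred.

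- Among referred: Link2CARE (0.20 × 0.50 + 0.20 × 0.25)/0.40 = 37.5%; SOC 50%; difference −12.5 points.
- Of all randomized: Link2CARE 0.10 + 0.05 = 15%; SOC 10%; difference +5 points.

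**3. A fuller model (assumed rates).** Motivation m is standard normal. A youth is referred when (m + noise)/√2 exceeds a threshold set by the arm's referral rate, with standard normal noise. Among referred youth, logit P(attend) = −0.8 + s·m + d, with d applying to Link2CARE only. Unreferred youth do not attend, except in step 6. Power is for a result favoring Link2CARE: normal approximation, unpooled variance, two-sided 0.05 unadjusted, 169 per arm, and 169 × referral rate within the referred. Values are SOC vs Link2CARE.

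| Assumptions | Referred | Attended, of referred | Power | Attended, of all randomized | Power |
|---|---|---|---|---|---|
| s = 1, no direct effect | 10% vs 40% | 59.6% vs 47.4% | <1% | 6.0% vs 18.9% | 96% |
| same | 20% vs 50% | 54.1% vs 44.8% | <1% | 10.8% vs 22.4% | 82% |
| same | 20% vs 25% | 54.1% vs 52.1% | 2% | 10.8% vs 13.0% | 9% |
| s = 0, no direct effect | 10% vs 40% | 31.0% vs 31.0% | 3% | 3.1% vs 12.4% | 90% |
| s = 1, direct odds ratio 2 | 10% vs 40% | 59.6% vs 62.3% | 4% | 6.0% vs 24.9% | >99% |
| same | 20% vs 50% | 54.1% vs 59.7% | 8% | 10.8% vs 29.9% | 99% |
| same | 20% vs 25% | 54.1% vs 66.8% | 20% | 10.8% vs 16.7% | 35% |
| same | 25% vs 25% | 52.1% vs 66.8% | 28% | 13.0% vs 16.7% | 16% |

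First row in full. Within referred, n = 17 vs 68: −0.122/√(0.596 × 0.404/16.9 + 0.474 × 0.526/67.6) = −0.122/0.134, so z = −0.91. The second row gives z = −0.92. Neither reversal is near significance.

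**4. Where reversal stops.** With s = 1 and no direct effect, the within-referred comparison points against Link2CARE in all three unequal-referral rows. It stops doing so at direct odds ratios of 1.76, 1.54 and 1.10 for the three pairs of referral rates. With s = 0.5 the gaps without a direct effect are −6.5, −4.9 and −1.1 points, and the break-even odds ratios are 1.32, 1.24 and 1.05.

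**5. The raw-count reading.** In the first row, counts of 225 per arm are 13 vs 43. There is no reversal and no selection problem.

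**6. Attendance without a study referral.** If 5% of unreferred youth attend anyway, at 10% vs 40% referral that is 225 × 0.90 × 0.05 = 10 SOC vs 225 × 0.60 × 0.05 = 7 Link2CARE youth. Ignoring them overstates the gain by (0.40 − 0.10) × 0.05 = 1.5 points; at 2%, by 0.6 points. They must be counted.

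**The case against.** The operative definitions of Domain 2(c) agree with each other, and the Aim 1 model is said to apply to the domains as listed. The restricting words sit in a list of examples and promise a greater number, not a greater proportion. Read as a count, they describe a referral-to-attendance cascade, which is sound over 1:1 arms. The missing numbered section may define the linkage variables. Referral is reported separately as Domain 2(b), so a referral gain would not vanish from the results. Reversal needs unequal referral, referral driven by motivation, and little direct effect, yet the brief intervention and navigator are meant to raise readiness and lower barriers. Attendance among youth who need treatment is also a legitimate question.

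Most of this stands. It makes the point an unresolved ambiguity rather than a flat contradiction. It does not remove the need for a decision: a count does not map directly onto a person-level model, and nothing in the document extends intent-to-treat to this outcome. If the missing section fixes the analysis set, the hypothesis need only be made to match it.

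A reader might infer that the plan commits to analyzing referred youth only, or that the trial is likely to report Link2CARE as harmful on linkage. The documents support neither. No sentence says the model is fitted to referred youth alone, and the reversals arise only under assumed rates and are not significant.

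**Conclusion.** The concern holds as an inconsistency in a secondary outcome that should be resolved before data are seen. If the model is fitted among referred youth, the comparison is not randomized and leaves out any gain from additional referrals. Under the assumed rates with referral of 10% vs 40% or 20% vs 50%, a gain of 9 to 19 points in the share of randomized youth attending becomes a within-referred difference between −12 and +6 points, with power of 8% or less. With referral of 20% vs 25% the distortion is small. With equal referral there is no bias, and the within-referred comparison has more power (28% vs 16%).

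The main risk is a missed gain. All rates are assumptions. The powers use unadjusted 0.05, whereas the plan promises familywise control for all hypothesis tests, so the higher ones are optimistic; the normal approximation is rough with 17 referred SOC youth. The primary outcomes, sample size and stopping rule are unaffected.

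**What to change.** 1. Delete the qualifier limiting the attendance hypothesis to referred youth, so that it matches Domain 2(c).
2. Define attendance (intake plus one session, y/n) for every randomized youth at each follow-up. Count any attendance, with or without a study referral. Count youth known not to have attended, including those never referred, as not attended.
3. Make the between-arm test on all randomized youth. State that the plan's multiple imputation, "employed to impute the missing endpoint for conducting the intent-to-treat analysis", covers this outcome.
4. Report attendance among referred youth descriptively only.
5. Reconcile Aim 1(c) in the same edit. Any comparison among youth with SU or disorder should be supportive, and defined only by a baseline measure taken in both arms, if one exists, not by the post-randomization Link2CARE screener.

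The cost is wording, plus possibly one follow-up item: all 450 youth are to be interviewed, but the interview content is not described. The absolute proportions will be smaller and less specific to youth in need, and some power is lost if the arms turn out to refer at equal rates.
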